6.2.2 Consent, Detailed Screening, Enrollment, Baseline, and/or Randomization

Consenting Procedure

All individuals agreeing to participate will provide written informed consent during Visit 1 (i.e., prior to beginning any study procedures). Subject consent procedures will be carried out by individuals designated and trained by each site PI and the IRB to carry out these procedures (i.e., the proposed research assistants). In the Consent Form, it will be emphasized that subjects may discontinue participating at any time and still receive prorated compensation. The recruiter will inform potential subjects that participation is completely voluntary, and they may withdraw at any time without penalty or running the risk of jeopardizing current and future treatment at the Rush or Vanderbilt medical centers. Consent forms with identifiable subject information will be maintained in a separate locked file from the actual study data files, which will be identified only by subject number. All subjects will be informed regarding how HIPAA requirements may impact on their study records, and will sign a notification regarding this issue. All published data will be reported in a manner in which individual data for specific subjects are not identifiable.

Screening

Screening can occur from 1 month prior to study enrollment to the day before study enrollment.

Screening evaluations will consist of:

- demographics
- confirmation of diagnosis of chronic low back pain
- pain duration and intensity ratings
- medical history
- list of current medications, prescribed dose and reported actual dose taken
- list of over the counter medications
- psychological screening: SCID-IV/NP

Please see sections 4.1 and 4.2 for inclusion/exclusion criteria. The criteria will be examined once all screening assessments are complete so as to not alert participants to our precise screening criteria.

Enrollment

The enrollment date is day the individual has met all the screening criteria and signs the informed consent form.

Baseline Assessment (Visit 1)

- Pain interference (primary outcome), pain intensity, negative affect (anger, anxiety, depression), physical function, sleep disturbance and social support will

be assessed via designated Patient-Reported Outcomes Measurement Information System (PROMIS) forms for each construct.

- Baseline demographics, neuropathy (painDETECT questionnaire), medication and healthcare use, opioid use (HOME Opioid Questionnaire), bothersome pain, back pain (McGill Pain Questionnaire) and disability (Oswestry Low Back Disability), and attitudes on changing pain (Pain Stages of Change Questionnaire) will also be assessed.
- Pain catastrophizing will be assessed with the Pain Catastrophizing Scale.
- Mindfulness will be assessed with the Five Facets of Mindfulness Questionnaire (short form), and the Multidimensional Assessment of Interoceptive Awareness (short form).
- Self-efficacy will be assessed with the Pain Self-Efficacy Questionnaire.
- Height and weight will be measured using a scale.
- Blood pressure will be measured using a Dinamap blood pressure monitor.

Pre-Treatment Lab Sessions (Visits 2 & 3)

- A urine sample will be collected and tested for opioids (using a rapid single panel opioid screening test) and pregnancy (females only – using an analog pregnancy test).
- Baseline assessment of opioid function and conditioned pain modulation will be assessed via the Quantitative Sensory Testing (QST) procedures described below.
- To enable potential future assessment of treatment-related changes in relevant biomarkers, a 4mL sample of whole blood will be drawn from the cannula placed for drug administration into a tube with EDTA prior to beginning laboratory pain or drug administration procedures in both laboratory sessions. Within 10 minutes of collection, samples will be centrifuged for 10 minutes at 3500rpm and 4°C. Plasma will then be pipetted into microcentrifuge tubes (0.5mL aliquots) and stored at -80°C until assayed.
- McGill Pain Questionnaire administered during the QST procedures in several versions to capture pain in back before and after each procedure.
- Evoked pain intensity and unpleasantness and naloxone side effects will be assessed.
- Assessment of any adverse events.

Endogenous Opioid (EO) Function

As in our previous work (68-72), we will use a placebo-controlled opioid blockade procedure to assess treatment-induced changes in EO function. Naloxone is an opioid antagonist with a brief half-life (1.1 hours; 78). We will use a weight-adjusted dose of 0.11 mg/kg with a maximum dose of 8mg (8mg dose for a 160 lb. individual,

consistent with our past work 69-71). As in our past studies, naloxone in 20 ml normal saline will be infused over a 10-minute period through an intravenous cannula placed in the non-dominant arm. At this dosage, naloxone provides effective blockade of all three major opioid receptor subtypes (79). Naloxone is FDA approved, and appears to have no clinical effects in non-opiate dependent individuals. Thus, participants using opioid analgesics on a daily basis or within 3 days of each laboratory session (confirmed via urine drug screen) and/or experiences withdrawal symptoms with the initial naloxone administration, will be excluded. It has been used safely at similar dosages in previous studies, including our studies in CLBP samples (68-72). Peak naloxone activity will be achieved approximately 10 minutes following completion of the infusion. A second dose of naloxone (0.055 mg/kg with a maximum dose of 4mg; 4mg for a 160 lb. individual) will be infused following the thermal and ischemic tasks (before CPM procedures). This dose will be used to maintain adequate opioid blockade across the duration of pain-induction procedures.

The QST protocol will use 2 laboratory pain tasks for evaluation of evoked pain responsiveness. An ischemic pain task will be used based on procedures described by Maurset et al. (80), similar to our past opioid blockade studies (68,72). Subjects will first engage in 2 mins of dominant forearm muscle exercise using a hand dynamometer at 50% of his or her maximal grip strength (as determined prior to beginning laboratory procedures), and then will be asked to raise the dominant forearm over their head for 15 secs. A blood pressure cuff will then be inflated on the participant's dominant biceps to 200 mmHg pressure, and the cuff will remain inflated until tolerance is reached, up to a maximum of 8 mins. As in our previous work (68,72), at 30-sec intervals throughout the ischemic task, participants will be asked to rate their current acute pain using a 0-100 verbal numeric rating scale (0 = "no pain" and 100 = "worst possible pain"). Pain threshold will be defined as time elapsed from task onset to when the sensation is first described as "painful." Pain tolerance will be defined as time elapsed between onset of the pain task and patients' expressed desire to terminate the task (8 min max). At tolerance, subjects will be asked to rate the overall ischemic task pain intensity using the McGill Pain Questionnaire (MPQ; see below).

A heat pain task using a Medoc TSAII NeuroSensory Analyzer (Medoc US., Minneapolis, MN) will then follow. This equipment will be used to assess heat pain threshold and tolerance using an ascending method of limits protocol as used in our prior work (68,71,72). The equipment to be used has a hardware temperature cutoff of 51°C in order to prevent tissue injury. Four trials each will be conducted for heat pain threshold and tolerance, with each trial conducted sequentially at 1 of 4 different non-overlapping sites on the non-dominant ventral forearm. An interval of 30 secs between successive stimuli will be employed. For threshold trials, the probe will start at an adaptation temp of 32°C, with the temp increasing at a ramp rate of 0.5°C/sec until the subject indicates that the stimulus has begun to feel "painful." For tolerance trials, the probe will start at an adaptation temperature of 40°C, with the temperature increasing at a ramp rate of 0.5°C/sec until the subject indicates maximum tolerance has been reached. Means of the 4 thermal pain threshold and tolerance trials will be derived for use in analyses. Immediately upon completion of the final heat pain tolerance trial, subjects will be asked to rate the overall pain experienced during this

trial using the MPQ. EO function will be operationalized as in our past work as changes in evoked pain responses between the placebo and naloxone conditions (68,71,72), with blockade effects on the visual analog scale (VAS) pain intensity measure of the MPQ considered primary.

Conditioned Pain Modulation (CPM)

Efficiency of descending inhibition of pain (i.e., CPM) will be assessed using a protocol adapted from Gehling et al. (81) which found that combining heat pain (test stimulus) with cold pressor pain (conditioning stimulus) demonstrated acceptable test-retest reliability over a 3 day test-retest interval. CPM is a centrally-mediated effect (107), and therefore is expected to be observed at sites throughout the body, e.g., CPM elicited with stimuli applied to the back vs. the forearm is similar (102). As is common in the CPM literature, and to avoid any local sensitization confounds with stimuli applied to the back in CLBP patients, the current project will apply both the test and conditioning stimuli in the periphery. A cold pressor task [circulating ice water bath; see our prior work (112,113)] applied to the nondominant upper extremity will be the tonic conditioning stimulus, and the same TSA-II heat pain stimulus used in thermal pain testing (applied to the dominant forearm) will be the test stimulus. At the beginning of lab session 1, we will determine the heat pain stimulus temperature corresponding with an intensity rating of 60/100 for that individual. This will be done using a series of brief (5 sec) thermal stimuli applied starting at 44°C, based on our prior work indicating a mean thermal pain threshold and tolerance of 44°C and 48°C respectively in chronic back pain patients. This stimulus intensity will be increased/decreased incrementally by 0.5°C until the targeted perceived pain intensity of 60/100 is reached. This temperature (referred to hereafter as P60) will be used as the stimulus intensity for the test stimulus in all CPM procedures. These CPM procedures will entail: (a) Three assessments of heat pain ratings (once every 10 sec) in response to 30 secs of a constant thermal stimulus applied at the predetermined P60 target temperature to the dominant arm (“Pre-Conditioning Phase”), (b) Initiation of the tonic cold pressor conditioning stimulus to the nondominant hand (immersion in an ice water bath) and after 30 sec of exposure to the conditioning stimulus, (c) Three assessments of heat pain ratings (once every 10 sec) in response to 30 secs of the P60 thermal test stimulus applied simultaneously with the conditioning stimulus (“Conditioning Phase”; the total cold pressor duration will be 60 seconds). Change in mean thermal stimulus pain ratings during the pre-conditioning minus conditioning phases will be used to index CPM.

Assessment of spinal stiffness

The VerteTrack device (VibeDx Diagnostic Corp) will be used to measure the lumbar posterior to anterior spinal stiffness, with L3 values considered primary per validation studies (40,103). The VerteTrack device has not been approved by the FDA. The device consists of a solid aluminum gantry (Width 108cm × Height 109cm × Length 151cm) on lockable casters that can be positioned over a participant lying in the prone position on a standard padded-plinth. Each assessment takes approximately 15 mins.

Two types of spinal stiffness values will be calculated from the force displacement data of each indentation: global stiffness and terminal stiffness. Global stiffness will be calculated from the slope of force displacement curve between 5 Newtons (N) and 60 N, representing the stiffness of underlying tissues throughout the indentation (39). Terminal stiffness is a ratio between the maximal applied force (60 N) and maximal resultant displacement, representing stiffness at the end of indentation (39). Spinal stiffness will be measured 3 times at each assessment. Averaging 3 measurements, within- and between-day reliability point estimates of both global and terminal stiffness were 0.99 and 0.98, respectively (40).

Randomization

Study subjects will be randomized to receive either MT or SMT. The order of drug administration for each laboratory session will also be randomized and counterbalanced (placebo vs. naloxone), and double-blinded. These randomizations will occur prior to the baseline screening visit (Visit 1). All randomization will be carried out using the Proc Plan procedure in SAS version 9.2 (SAS Institute, Cary, NC). This SAS procedure will be used to generate a randomization schedule for each sequential study slot (MT vs. SMT and the order of naloxone/placebo administration in each set of lab visits). Study subjects will be assigned to these previously randomized study slots in the order that they are enrolled, and the previously determined randomization status associated with each slot will determine the study condition each subject is in and the order of drug administration.

6.2.3 Blinding

Research staff at each site who will conduct weekly phone assessments (when applicable) and who will conduct the laboratory pain-induction sessions will be blind to subject treatment condition. The randomization scheme will be implemented by department administrative assistants who will have no other role in the study.

Given the nature of the interventions and that Co-Is Drs. [name] and [name] will be providing intervention-specific oversight (e.g., review of MT and SMT audio- and video-recordings), neither of these Co-Is will be blinded as to intervention assignment. These individuals will not be engaged in review of individual level study data or analysis of study results. The PIs (Drs. [name] and [name]) will be blinded to intervention assignment. Moreover, during routine review of data, PIs and other research staff will also be blinded to participant intervention assignment by hiding from view the columns denoting subject ID and intervention status in the REDCap database.

Double blinding (patient and investigators) as to drug condition for all laboratory sessions will be maintained by the Investigational Pharmacy at each site. Drug blinding will be broken by the PIs for specific participants as needed in the event of possible safety or side effect issues.

Participants will not be blinded to treatment condition: the MT and SMT procedures will be obvious.

Stake Holder	Intervention Group Assignment	Lab Drug Condition	Primary Mechanistic Outcome Measure	Clinical/Functional Outcome Measure
Study Subjects/Patients	Unblinded	Blinded	Unblinded	Unblinded
Instructors/Practitioners	Unblinded	Blinded	Blinded	Blinded
Outcome Assessors	Blinded	Blinded	Unblinded	Unblinded
Statistician	Blinded	Blinded	Unblinded	Unblinded
Principal Investigators	Blinded	Blinded	Blinded	Blinded

6.2.4 Treatment Visits

Treatment Sessions 1-8 (Visits 4, 5, 6, 7, 8, 9, 10, 11)

- MT and SMT treatments (as assigned) will be conducted during these visits.
- Assessment of spinal stiffness pre- and post-session as described above.
- Patient engagement in session will be rated by therapist.
- Assessment of any adverse events.

Assessed via phone call by RA within 48 hours of session or online via REDCap by the patient:

- Pain interference (primary outcome), pain intensity, negative affect (anger, anxiety, depression), physical function, sleep disturbance and social support will be assessed via designated PROMIS measures.
- Pain catastrophizing will be assessed with the Pain Catastrophizing Scale.
- Mindfulness will be assessed with the Five Facets of Mindfulness Questionnaire (short form), and the Multidimensional Assessment of Interoceptive Awareness (short form).
- Self-efficacy will be assessed with the Pain Self-Efficacy Questionnaire.
- Bothersome pain and attitudes on changing pain (Pain Stages of Change Questionnaire) will also be assessed.

Treatment sessions 3 and 6

In addition to the measures above, the following measures will be given:

- The Working Alliance Inventory – short form, and the Scale to Assess Therapeutic Relationships – Patient Version will be administered in-person.
- The Reaction to Treatment Questionnaire will be administered in-person.

Post-Treatment Lab Sessions (Visits 12, 13)

- A urine sample will be collected and tested for opioids (using a rapid single panel opioid screening test) and pregnancy (females only – using an analog pregnancy test).
- Post-treatment endogenous opioid function and conditioned pain modulation will be assessed via the QST procedures described in Section 5.2.
- To enable potential future assessment of treatment-related changes in relevant biomarkers, a 4mL sample of whole blood will be drawn from the cannula placed for drug administration into a tube with EDTA prior to beginning laboratory pain or drug administration procedures in both laboratory sessions. Within 10 minutes of collection, samples will be centrifuged for 10 minutes at 3500rpm and 4°C. Plasma will then be pipetted into microcentrifuge tubes (0.5mL aliquots) and stored at -80°C until assayed.
- McGill Pain Questionnaire administered during the QST procedures.
- Evoked pain intensity and unpleasantness and naloxone side effects will be assessed.
- Assessment of any adverse events.

6.2.5 Follow-up Visits

Follow-ups 3-month & 6-month (Visits 14 & 15)

- Pain interference (primary outcome), pain intensity, negative affect (anger, anxiety, depression), physical function, sleep disturbance and social support will be assessed via PROMIS item banks.
- Pain catastrophizing will be assessed with the Pain Catastrophizing Scale.
- Mindfulness will be assessed with the Five Facets of Mindfulness Questionnaire (short form), and the Multidimensional Assessment of Interoceptive Awareness (short form).
- Self-efficacy will be assessed with the Pain Self-Efficacy Questionnaire.
- Bothersome pain and attitudes on changing pain (Pain Stages of Change Questionnaire) will also be assessed.
- Assessment of any adverse events.

6.2.6 Missed Evaluations

There is a 6-week window from baseline (visit 1) to the first lab session (visit 2). The first lab session (visit 2) must occur within this window and the second lab session (visit 3) must be within 2 weeks of the first. The first treatment visit (visit 4) is to

occur within one week from lab session 2 (visit 3).

If a participant misses an intervention session (MT or SMT) the staff will attempt to reschedule the visit for the following week, and the treatment schedule will be adjusted accordingly.

Treatment sessions 1-4 (visits 4-7) must all occur within 2 months of lab session 2 (visit 3). The first post-treatment lab session (visit 12) should occur within one month from treatment session 8 (visit 11).

The second post treatment lab session (visit 13) must occur within 2 weeks of the first post treatment lab session (visit 12).

The date of the follow-up assessments will be calculated from the date of the final post treatment lab session (visit 13). Participants will have a 2-week window around this date to complete the 3- and 6-month follow-ups (visits 14 & 15). Failure to complete these assessments within this window will result in the follow-ups being skipped.

All visits that fall outside of these allowable windows will be reported as protocol deviations.

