8. INTERVENTION DISCONTINUATION

This study will be stopped prior to its completion if: (1) the intervention is associated with adverse effects that call into question the safety of the intervention; (2) difficulty in study recruitment or retention will significantly impact the ability to evaluate the study endpoints; (3) any new information becomes available during the trial that necessitates stopping the trial; or (4) other situations occur that might warrant stopping the trial.

Other potential reasons for early termination may include individual participant gross noncompliance (e.g., not responding to phone calls from staff, several cancellations of treatment appointments, no-shows to treatment appointments). Participants will also be discontinued if study investigators see a >25% worsening of baseline pain and mood during the MT or SMT treatments.

Participants will be monitored during the course of the study for evidence of significant deleterious physical, pain-related or emotional changes. In the event that a participant is judged by the research assistants and/or PIs to be deteriorating significantly in terms of pain and emotional condition as a result of their participation in this study, the team may decide to withdraw the subject from the trial and refer them for appropriate treatment. Participants will also be informed that should any unexpected or significant deleterious changes in their condition occur, that they immediately call [name] or [name] (PhD licensed clinical psychologists). Subjects will be given the office phone numbers of Drs [name] and [name] to ensure access to study staff. Drs. [name] and [name] will determine whether referrals to other healthcare providers are appropriate. Any necessary referrals will be made through telephone contact by the PIs to the appropriate practitioner. Therefore, a standardized referral form is not considered adequate for this study. The PIs will personally monitor all such referrals and document them accordingly. Such documentation will be kept confidential in the locked data storage area in Drs. [name]' or [name]'s office.

If a participant experiences a SAE, he/she will be discontinued in the study.

For the purposes of intent-to-treat analyses, we will make every effort to obtain scheduled follow-up assessments for all individuals failing to complete the study for any reason.

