9.3 Definition of Populations

The ITT (intent to treat) sample will be all subjects who complete baseline measures. The “per protocol” sample (i.e., “treatment completers”) will be those subjects who complete at least 6 of the 8 treatment sessions.

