9.5.1 Primary Outcome

Our primary mechanism outcome is pre- to post treatment changes in EO function.

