9.6 Data Analyses

Primary analyses will be conducted on an ITT basis.

Aim 1: To determine the degree to which MT and SMT produce effects in nonspecific mechanisms.

The primary analyses will employ the two-sample t-test to compare mean change in each nonspecific mechanism within a noninferiority test construct to compare mean change in outcome from pre to post treatment between the two treatment arms. An overall, 2-sided, significance level of 0.05 will be used. Linear mixed models will be used as a supplemental analysis, allowing us to utilize all data collected, account for within subject variation, and model changes over time. The fixed effect part of the model will be

$Mechanism_{ij} = \beta_0 + \beta_1 Time_{ij} + \beta_2 Tx_i + \beta_3 (Tx_i * Time_{ij}) + \varepsilon_{ij}$ for subject i at visit j.

If β_3 is significantly negative ($p < .05$), this would indicate that the mechanism variable decreased more in SMT than in MT (Fitzmaurice, Laird, & Ware, 2011). In case of a significant interaction, we will test simple slopes of Time for each Treatment Condition separately AND by testing post treatment differences between MT and SMT controlling for pre-treatment values.

Candidate covariance structures will be assessed using the data's correlation structure and Akaike's Information Criterion (AIC). Random coefficients (e.g. random intercept and/or random slope) will be included in the model if they significantly improve the model fit as determined by the likelihood ratio test. Standardized residuals and Cook's distance will be used to assess the influence of outliers and individual observations. Residual plots will be used to check the multivariate normal distribution assumption. The pattern of missing data will be examined to determine its missing mechanism and the amount. If data are missing not at random (MNAR), data imputations may be used. If other deviations from the model assumptions are detected, appropriate measures will be taken to prevent inferential bias, e.g. data transformations and use of bootstrap techniques to compute standard errors.

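### The protocol skips 3- and 6-month follow-ups that miss a 2-week window and dates them only from Visit 13, so late questionnaires are not collected and early leavers have no follow-up date

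*Protocol*

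**What the plan says.** Section 6.2.6 (Missed Evaluations) gives one anchor for long-term follow-up: "The date of the follow-up assessments will be calculated from the date of the final post treatment lab session (visit 13". It allows a 2-week window around each due date, without saying whether this means one week or two on either side. It then states: "Failure to complete these assessments within this window will result in the follow-ups being skipped". The next sentence reads: "All visits that fall outside of these allowable windows will be reported as protocol deviations". The section gives no other anchor for someone without a Visit 13.

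Section 8 says that, for intention-to-treat purposes, "we will make every effort to obtain scheduled follow-up assessments for all individuals failing to complete the study for any reason". Section 9.3 defines the population: "The ITT (intent to treat) sample will be all subjects who complete baseline measures". Section 9.6 adds: "Primary analyses will be conducted on an ITT basis".

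Section 3 gives the 3- and 6-month data a scientific role, suggesting that a mechanism's value may show only in gains sustained to six months. Section 6.2.5 lists self-report measures, including pain interference (the primary clinical outcome), plus an adverse event check at these visits.

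**The concern.** Two features of one rule cause the difficulty.

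- **The skip rule governs collection, not analysis.** Once a questionnaire has been skipped, no later analysis plan can recover it. The measures are self-report, so obtaining one some days late costs little. Skipping also drops that visit's adverse event check.
- **The single anchor leaves some participants undated.** Someone who leaves before Visit 13 has nothing from which a due date can be calculated, yet belongs to the group that section 8 undertakes to pursue.

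At stake are the completeness and precision of the 3- and 6-month data. There is also a risk of selective loss. Section 8 lists worsening pain and mood, serious adverse events and gross noncompliance as grounds for discontinuation, and people who are hard to reach are plausibly those who miss a short window.

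**Working it through.** **1. The plan's own retention figure.** Inputs are 240 completers and 16% dropout (Précis, section 9.1).

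- 240 / (1 − 0.16) = 285.7, rounded up to 286.
- Check: 286 × 0.84 = 240.2.

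The stated 286 reproduces.

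**2. Ceiling on participants without an anchor.** 286 − 240 = 46, or 16%. All 46 lack a Visit 13 only if every dropout happens before it. The Précis counts 240 as completing follow-up, so the 46 also include people lost after Visit 13, who do have a date. These losses are already allowed for in the step from 286 to 240.

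**3. How much timing spread the plan already accepts.** Section 6.2.6 puts Visit 12 within one month of session 8, and Visit 13 within 2 weeks of Visit 12. One month is 365.25 / 12 / 7 = 4.35 weeks.

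- Lag from session 8 to Visit 13: 0 to 4.35 + 2 = 6.35 weeks.
- 3 months = 13.04 weeks; 6 months = 26.09 weeks.

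| Follow-up, in weeks after session 8 | Window read as ±1 week | Window read as ±2 weeks |
|---|---|---|
| 3-month, earliest | 13.04 − 1 = 12.0 | 13.04 − 2 = 11.0 |
| 3-month, latest | 6.35 + 13.04 + 1 = 20.4 | 6.35 + 13.04 + 2 = 21.4 |
| 6-month, earliest | 26.09 − 1 = 25.1 | 26.09 − 2 = 24.1 |
| 6-month, latest | 6.35 + 26.09 + 1 = 33.4 | 6.35 + 26.09 + 2 = 34.4 |

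Measured from the end of treatment, in-window assessments can differ by 8.35 weeks (±1) or 10.35 weeks (±2). An assessment a few days past the window is nevertheless skipped.

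**4. Illustration of lost precision.** The protocol gives no skip rate, so the fractions below are assumptions. If a further fraction f of the 240 is skipped, the standard error grows by 1/√(1 − f) − 1.

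| Assumed f | Participants left | Rise in standard error |
|---|---|---|
| 5% | 228 | 2.6% |
| 10% | 216 | 5.4% |
| 15% | 204 | 8.5% |
| 20% | 192 | 11.8% |

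**5. What is not affected.** Section 9.5.1 states: "Our primary mechanism outcome is pre- to post treatment changes in EO function". Sections 9.5.2 and 9.6 also work with pre-post, pre-mid-post or weekly data. The power figures in section 9.2 rest on 120 per arm for pre-post changes. The Aim 1 figure reproduces at 0.851 (margin ±3.0, SD 7.5), and the skip rule does not alter it.

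**The case against.** The best defence is that the two sections can be read together. Section 8 is a best-efforts statement about assessments on the schedule, and section 6.2.6 sets that schedule. Staff could try hard within the window, then stop, and breach neither. This has force for late attenders, so the relation is a tension and not a flat contradiction. It does not help those without a Visit 13, for whom there is no schedule to apply.

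Other points on that side stand:

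- A reader might infer that everyone who stops treatment early lacks Visit 13. The protocol does not say so. Participants with fewer than 6 of 8 sessions remain in the intention-to-treat sample, and nothing bars them from the post-treatment laboratory sessions.
- A reader might infer that usable data are thrown away. They are not collected in the first place.
- A reader might infer that the 3- and 6-month results are biased. Nothing shows that loss differs by arm, and the weekly measurements of many of the same scales could support a mixed model under a missing-at-random assumption.
- A fixed window that keeps assessments comparable is a legitimate aim. However, the spread in step 3 shows that the window secures little comparability in time since treatment.

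Dating early leavers from their last attended session would place them systematically earlier than completers. The remedy should avoid that.

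**Conclusion.** The point holds in limited form. Section 6.2.6 forgoes late self-report data by rule and leaves participants who exit before Visit 13 without a follow-up date. This is in tension with section 8 and poorly matched to the 8 to 10 weeks of spread that the same section already tolerates.

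The effect is confined to the 3- and 6-month outcomes. The primary outcome and every stated power figure are unaffected. The size of the loss cannot be derived from the protocol: 46 of 286 is a ceiling on missing anchors and is not additional to planned dropout, while the 2.6% to 11.8% rise in standard error rests on an assumed 5% to 20% skip rate. Selective loss is plausible, but bias is not demonstrated. The change should be made because it is cheap and the data cannot be recovered afterwards.

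**What to change.** Reconcile sections 6.2.6 and 8 as follows.

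1. Replace the skip rule with collection of late follow-up questionnaires by phone or online, reported as protocol deviations as section 6.2.6 already provides for out-of-window visits.
2. Analyse every follow-up at its actual assessment time, with an in-window-only analysis as sensitivity.
3. For participants without Visit 13, schedule follow-up from the date on which Visit 13 would have been planned, and state how that date is calculated. This keeps their timing comparable with that of completers.
4. State whether the 2-week window means one week or two on either side.

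The cost is protocol wording, a few later surveys, and slightly more spread in assessment times.
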